5.1.1 Percentage of Time <54 mg/dL (Non-Inferiority)

The hypotheses associated with this endpoint are:

- o H₀: μ₁ μ_C ≥ 1
- ο H_A: μι μc < 1

where μ_l and μ_c are the population means of per-participant percentage of time <54 mg/dL as measured by the study CGM during the 13 weeks in the Intervention and Control groups, respectively

The non-inferiority margin will be set to 1%. The calculation of percentage of time in a specified range is described in Section 7.4. If the upper bound of the two-sided 95% confidence interval (corresponding to 1-sided 97.5% CI) for the difference (μ_I minus μ_C) is <1%, non-inferiority will be established. If the upper bound of the two-sided 95% confidence interval for the difference (μ_I minus μ_C) is <0%, superiority of the Intervention group compared to the Control group will be established.

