3.2 SECONDARY EFFECTIVENESS OBJECTIVE AND ENDPOINTS

The secondary objective is to demonstrate additional measures of efficacy and safety of the Omnipod 5 System compared to pump and CGM therapy in adults with type 1 diabetes The secondary endpoints associated with this objective will be compared between the Intervention arm and the Control arm:

- Percentage of time <54 mg/dL (non-inferiority) during the 13 weeks of randomized period
- Percentage of time >180 mg/dL during the 13 weeks of randomized period
- Mean glucose during the 13 weeks of randomized period
- Change from baseline in A1C at 13 weeks
- Percentage of time < 70 mg/dL during the 13 weeks of randomized period
- Change from baseline in Type 1-Diabetes Distress Scale (T1-DDS) total score at 13 weeks
- Change from baseline in Hypoglycemia Confidence Scale (HCS) total score at 13
 weeks
- Change from baseline in Diabetes Quality of Life-brief (DQOL-brief) total score at 13 weeks
- Proportion of participants achieving a minimally clinically important difference (MCID) of ≥0.19 points (improvement) on the T1-DDS questionnaire total score at 13 weeks
- Proportion of participants achieving a clinically meaningful improvement in the DQOL-brief total score after 13 weeks
- Proportion of participants achieving HCS total score of ≥3 after 13 weeks

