3.3 EXPLORATORY ENDPOINTS

The following exploratory endpoints will be evaluated and compared in the Intervention group vs. Control group at the end of the 13 weeks:

- Proportion of participants with A1C <7%
- Proportion of participants with A1C <8%
- Proportion of participants with $\geq 1\%$ improvement in A1C from baseline
- Proportion of participants with ≥10 percentage point relative improvement in A1C from baseline
- Proportion of participants with either ≥1% improvement in A1C from baseline OR
 ≥10 percentage point relative improvement in A1C from baseline
- Change from baseline in Body Mass Index (BMI)
- Change from baseline in total daily insulin (TDI) (units/kg)
- Additional CGM-derived endpoints, such as coefficient of variation, time above range >250 mg/dL, percentage of time < 54 mg/dL (superiority), TIR during daytime and nighttime hours
- Number of episodes of severe hypoglycemia
- Number of episodes of DKA

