4 ANALYSIS OF PRIMARY ENDPOINT

4.1 SAMPLE SIZE

The sample size estimation is based on the following assumptions:

- Power of 90% and two-sided significance level of 5%
- Difference between groups of 10% in TIR 70-180 mg/dL
- Standard deviation of 16.5% in each group
- 2:1 randomization (Intervention:Control)

Under these assumptions, a total sample size of 131 participants is required (87 Intervention, 44 Control). To allow for pre-randomization attrition of up to 15%, and post-randomization attrition of up to 22.9%, a total sample size of up to 200 will be enrolled to give 170 participants randomized and 131 participants completing the 13 weeks. The anticipated difference in TIR 70-180 mg/dL was projected from the OP5 pivotal study.

The sample size calculations were performed using PASS 2021.

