5 ANALYSIS OF OTHER ENDPOINTS

5.1 ANALYSIS OF SECONDARY ENDPOINTS (PERIOD 1)

To preserve the family-wise type 1 error for selected key secondary endpoints, a fixed sequence hierarchical testing approach will be used. If the primary endpoint is found to be statistically significant at a two-sided significance level of 5%, testing for secondary endpoints can commence. Secondary endpoints will be tested in a hierarchical fashion at a one-sided significance level of 2.5% (or two-sided significance level of 5% as appropriate). Each endpoint with a two-sided p-value ≤ 0.05 (or one-sided p-value of ≤ 0.025 , as appropriate) is considered to be met until a secondary endpoint with a two-sided p-value ≥ 0.05 (or one-sided p-value of ≥ 0.025 , as appropriate) is encountered. This process continues iteratively moving to the next endpoint down on the list until a non-significant result is observed, or all endpoints have been tested. If a non-significant result is encountered, then formal statistical hypothesis testing is terminated and any variables below on the list are not formally tested.

Regardless of the results of the hierarchical testing, summary statistics appropriate to the distribution will be tabulated for each key secondary endpoint by treatment group. A 95% confidence interval for the treatment effect will also be calculated for all key secondary outcomes listed above. However, a confidence interval that is below zero (superiority) or that is below the non-inferiority margin (noninferiority) will not be considered a statistically significant result if an outcome variable higher on the hierarchical list failed to reach statistical significance.

The secondary endpoints will be analyzed using a repeated measures linear mixed effects model with the endpoint at baseline and at 13 weeks as the dependent variable. The correlation between baseline and follow-up will be modelled using an unstructured covariance matrix. The model will include randomized treatment group, age, sex, and duration of diagnosis as fixed effects and site as a random effect. This model adjusts for baseline value of the endpoint by forcing the treatment groups to have the same mean value at baseline. Missing data will be handled by using a direct likelihood approach which will allow participants to be included even if they only have data at one of the time points.

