5.1.8 Change from Baseline in DQOL-brief Total Score

The hypotheses associated with this endpoint are:

- Η₀: μ₁ μ_C = 0
- HA: $\mu_1 \mu_c \neq 0$

where μ_1 and μ_c are the population means of change from Baseline (Visit 2) in DQOL-brief total score after 13 weeks in the Intervention and Control groups, respectively; change from baseline is calculated as follows: *Change from Baseline in DQOL-brief = DQOL-brief (13 weeks) – DQOL-brief (Visit 2)*

The Diabetes Quality of Life-brief is further described in Section 7.7.

5.1.9 Proportion of Participants with T1-DDS MCID (Total Score Improvement ≥0.19) after 13 Weeks

The proportion of participants achieving a minimally clinically important difference (MCID) of ≥ 0.19 points (improvement) on the T1-DDS questionnaire total score at 13 weeks will be compared between treatment groups. [1] Those hypotheses are stated as:

- H₀: $\pi_{I} \pi_{C} = 0$
- $\circ \quad H_A: \pi_I \pi_C \neq 0$

where π_l and π_c are the proportion of participants achieving an improvement of ≥ 0.19 points after 13 weeks in the Intervention and Control groups, respectively.

This endpoint will be considered met if the treatment group fixed effect in the logistic regression is significant at a two-sided significance level of 5%.

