5.2.4 Additional CGM-Derived Endpoints

The following additional CGM-derived endpoints, such as coefficient of variation (CV), percentage of time >250 mg/dL, percentage of time <54 mg/dL (superiority), TIR during daytime and nighttime hours will be compared between groups at the end of the 13-week randomized period.

CV is calculated per participant as follows, then summarized and compared between groups:

$$CV(\%) = \frac{SD \ of \ glucose}{mean \ glucose}$$

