5.2.6 Analysis Methods for Exploratory Endpoints

The mITT analysis set will be the main analysis set used to analyze these endpoints.

For continuous endpoints, mean and standard deviation or median and interquartile range, as appropriate, in each group will be presented. Continuous endpoints will be analyzed using a repeated measures linear mixed effects with the endpoint at baseline and at 13 weeks as the dependent variable. The correlation between baseline and follow-up will be modelled using an unstructured covariance matrix. The model will include randomized treatment group, age, sex, and duration of diagnosis as fixed effects and site as a random effect. This model adjusts for baseline value of the endpoint by forcing the treatment groups to have the same mean value at baseline. If values are highly skewed, then robust regression using M-estimation will be used instead, as described above for the secondary endpoints.

For binary endpoints, number and percent of participants in each group will be presented. Binary endpoints will be analyzed using a logistic mixed effects model with the endpoints as the outcome. The following variables will also be included in the model as fixed effects: randomized treatment group, age, sex, duration of diagnosis, and baseline continuous value of the outcome being tested. In addition, the model will adjust for site as a random effect. A 95% confidence interval for the treatment group adjusted risk difference will be produced using parametric bootstrapping. Analysis of binary endpoint will be based on complete cases only.

Since the results of exploratory endpoint analyses will not be used to support clinical claims, no adjustment for multiplicity will be performed.

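### Superiority on time below 54 mg/dL is both a claim inside the error-controlled sequence and an exploratory analysis; if claimed as confirmatory, the family-wise error can exceed 5%

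*SAP*

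**What the plan says.** SAP 5.1 sets up a fixed sequence to protect the family-wise error: the primary at two-sided 5%, then each secondary endpoint at two-sided 5% or one-sided 2.5%. Step 1 (SAP 5.1.1) is time below 54 mg/dL, with a single pair of hypotheses and a 1-point non-inferiority margin. The same section then says that if the upper limit of the two-sided 95% interval is below 0%, "superiority of the Intervention group compared to the Control group will be established". Protocol 11.2 and 11.8 carry the same rule, and 11.8 does so under a promise of strict type I error control.

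Other parts of the SAP give the comparison a different status:

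- SAP 3.2 lists the secondary endpoint as "Percentage of time <54 mg/dL (non-inferiority) during the 13 weeks of randomized period", with no mention of superiority.
- SAP 3.3 lists "percentage of time < 54 mg/dL (superiority)" among the exploratory endpoints, and SAP 5.2.4 repeats it.
- SAP 5.2.6 states: "Since the results of exploratory endpoint analyses will not be used to support clinical claims, no adjustment for multiplicity will be performed".

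The protocol also lists it as exploratory (Protocol Summary, 6.3 and 11.3), and 11.8 says exploratory endpoints are not formally tested.

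**The concern.** One comparison cannot be both a conclusion drawn inside an error-controlled sequence and an analysis barred from supporting claims. As written, the choice between the two could be made after the result is known. Time below 54 mg/dL is a hypoglycaemia safety measure, so confirmed superiority on it would be an attractive statement to make.

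The error rate is also at stake. Reading non-inferiority and then superiority from one 95% interval costs no alpha, because the two hypotheses are nested. The difficulty is that the sequence goes on to time above 180 mg/dL once non-inferiority is met, and no text makes that step wait for superiority. A confirmatory superiority claim would therefore sit beside the chain, with no numbered position and no share of alpha.

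**Working it through.** **Does any rule in the documents settle the status?**

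- Precedence of the SAP over the protocol (SAP 1, protocol 12.7) does not help, because SAP 5.1.1 conflicts with SAP 3.3, 5.2.4 and 5.2.6.
- SAP 5.1 says that an interval below zero "will not be considered a statistically significant result if an outcome variable higher on the hierarchical list failed to reach statistical significance". For step 1 only the primary is higher, so this leaves the confirmatory reading open.
- The three binary questionnaire follow-ups, which protocol 11.8 nests under their parent endpoints, are listed in SAP 3.2 and have numbered steps 5.1.9 to 5.1.11. Each has its own hypotheses and success rule ("This endpoint will be considered met if the treatment group fixed effect in the logistic regression is significant"). Superiority on time below 54 has none of these. This points to the exploratory reading, but the sentence in 5.1.1 still says otherwise.

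**Plan's own figure.** SAP 4.1 assumes "Power of 90% and two-sided significance level of 5"%, a 10-point difference in time in range, SD 16.5 and 87/44 participants. A two-sample t-test with these inputs has power 90.2%, so the stated sample size of 131 is reproduced.

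**Error rate under the confirmatory reading.** Scenario: the primary effect is real, the true difference in time below 54 is 0, and one later two-sided endpoint that is reached is a true null. Let Z1 be the time-below-54 statistic and Z2 the later one, bivariate normal with correlation r, and z = 1.96.

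If the primary and non-inferiority are sure to pass, error = 1 − P(Z1 ≥ −z and |Z2| ≤ z). For r = 0 this is 1 − 0.975 × 0.95 = 7.375%. The upper bound is 2.5% + 5% = 7.5%.

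| r (assumed) | 0 | 0.3 | 0.5 | 0.7 | 0.9 |
|---|---|---|---|---|---|
| Error | 7.4% | 7.3% | 7.0% | 6.7% | 6.0% |
| × 0.90 primary power | 6.6% | 6.5% | 6.3% | 6.0% | 5.4% |

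The second row treats the primary as independent of the rest. The likeliest later null is time below 70 mg/dL. It contains time below 54, so r of 0.7 to 0.9 is the more relevant range.

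**Allowing non-inferiority to fail.** The documents give no SD for time below 54, so a range is assumed, with 87/44 completers: SE = SD × √(1/87 + 1/44) = 0.185 × SD. The chain continues only if Z1 < 1/SE − z, so

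error = P(Z1 < −z) + P(−z ≤ Z1 < 1/SE − z and |Z2| > z).

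| Assumed SD (points) | P(non-inferiority) | r = 0 | r = 0.7 | r = 0.9 |
|---|---|---|---|---|
| 1.0 | 0.9997 | 7.4% | 6.7% | 6.0% |
| 1.5 | 0.95 | 7.1% | 5.4% | 4.0% |
| 2.0 | 0.77 | 6.2% | 4.5% | 3.5% |
| 3.0 | 0.44 | 4.6% | 4.1% | 3.5% |

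The error falls to 5% at an SD of about 2.7 (r = 0), 1.7 (r = 0.7) or 1.3 (r = 0.9). With 90% primary power these become 2.3, 1.5 and 1.2.

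**Repairs checked.** In 2,000,000 simulated trials at r = 0, 0.5, 0.7 and 0.9, placing superiority last in the sequence gave an error of 5.0%. Placing it directly after non-inferiority, as a step that must be passed, gave 2.5%.

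**The case against.** The strongest reply is that the plan nearly settles the matter. The endpoint is titled and hypothesised as non-inferiority only, superiority is named in the exploratory lists, and 5.2.6 bars claims from them. On that reading the error stays at 5% and one stray sentence remains. This is fair, and it is why the preferred repair is wording only. It does not make the sentence harmless, because 5.1.1 uses for superiority the same language of establishment that it uses for the confirmatory non-inferiority conclusion.

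Second, the figures above 5% count later false results in either direction. Counting only false claims in favour of the Intervention group, with non-inferiority sure to pass, the error is 1 − 0.975² = 4.94% at r = 0, 4.2% at r = 0.7 and 3.5% at r = 0.9. This qualification stands. But the plan's stated level is two-sided 5%, and these values still exceed the matching one-sided 2.5%.

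Third, the size rests on several assumptions: the less favoured reading, a difference of exactly zero, a later null that is reached, an SD and a correlation. To reach time below 70, time above 180, mean glucose and A1C must all be significant first. The SD cut-offs also describe an unadjusted comparison of completers, whereas the plan uses a baseline-adjusted model in all randomised participants. With an assumed 113/57 split of 170, the error at SD 1.5 and r = 0.7 is 6.05% rather than 5.44%. The cut-offs are therefore approximate.

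**Conclusion.** The concern holds and should be fixed. The contradiction is in the text of both documents and cannot be resolved from either.

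The effect on error control is conditional. Under the exploratory reading there is none. Under the confirmatory reading the family-wise error can reach about 7.4% (bound 7.5%) for an unrelated later null. It is 6.7% to 6.0% for a null correlated 0.7 to 0.9 with time below 54, when non-inferiority is nearly certain. There is no excess if the SD of time below 54 is large enough that non-inferiority often fails. The interval rule itself is sound; the excess comes only from letting the chain continue without superiority. The primary test and the definition of study success in SAP 2.4 are unaffected.

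**What to change.** Preferred, because it matches SAP 3.2, 3.3 and 5.2.6: delete the superiority sentence from SAP 5.1.1 and from protocol 11.2 and 11.8, or state there that the comparison is exploratory. This costs wording only; the sponsor gives up a confirmatory superiority claim on time below 54 mg/dL.

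Alternative, if that claim is wanted:

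- remove the comparison from the exploratory lists (SAP 3.3 and 5.2.4; Protocol Summary, 6.3 and 11.3);
- add it, with its own hypotheses, to the secondary lists (SAP 3.2; Protocol Summary, 6.2.1 and 11.2);
- give it a numbered step fixed in advance, and align protocol 11.8.

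Last place, after SAP 5.1.11, is valid. Directly after non-inferiority is also valid, but every later endpoint would then depend on showing superiority. This option changes the testing procedure in both documents. Neither option changes the sample size or the primary test.

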5.1.2 Percentage of Time >180 mg/dL

The hypotheses associated with this endpoint are:

- $H_0: \mu_1 \mu_C = 0$
- o H_A: μ_I μ_C ≠ 0

where μ_1 and μ_c are the population means of per-participant percentage of time <180 mg/dL as measured by the study CGM during the 13 weeks in the Intervention and Control groups, respectively

The calculation of percentage of time in a specified range is described in Section 7.4.

5.1.3 Mean Glucose

The hypotheses associated with this endpoint are:

- $H_0: \mu_I \mu_C = 0$
- H_A: μι μc ≠ 0

where μ_l and μ_c are the population means of per-participant mean glucose as measured by the study CGM during the 13 weeks in the Intervention and Control groups, respectively

5.1.4 Change from Baseline in A1C

The hypotheses associated with this endpoint are:

- $H_0: \mu_1 \mu_c = 0$
- o H_A: μ_I μ_C ≠ 0

where μ_1 and μ_c are the population means of change from baseline (Visit 1) in A1C after 13 weeks in the Intervention and Control groups, respectively; change from baseline is calculated as follows:

Change from Baseline in A1C = A1C (Visit 1) – A1C (13 weeks)

5.1.5 Percentage of Time <70 mg/dL

The hypotheses associated with this endpoint are:

- Η₀: μ₁ μ_C = 0
- o H_A: μ i μ c ≠ 0

where μ_1 and μ_c are the population means of per-participant percentage of time <70 mg/dL as measured by the study CGM during the 13 weeks in the Intervention and Control groups, respectively

The calculation of percentage of time in a specified range is described in Section 7.4.

5.1.6 Change from Baseline in T1-DDS Total Score

The hypotheses associated with this endpoint are:

- Η₀: μ₁ μ_C = 0
- o H_A: μ_I μ_C ≠ 0

where μ_l and μ_c are the population means of change from Baseline (Visit 2) in T1-DDS total score after 13 weeks in the Intervention and Control groups, respectively; change from baseline is calculated at follows:

Change from Baseline in T1-DDS = T1-DDS (13 weeks) – T1-DDS (Visit 2)

The Type-1 Diabetes Distress Scale is further described in Section 7.7.

5.1.7 Change from Baseline in HCS Total Score

The hypotheses associated with this endpoint are:

- $H_0: \mu_1 \mu_C = 0$
- H_A: μ_I μ_C ≠ 0

where μ_1 and μ_c are the population means of change from Baseline (Visit 2) in HCS total score after 13 weeks in the Intervention and Control groups, respectively; change from baseline is calculated as follows: *Change from Baseline in HCS = HCS (13 weeks) – HCS (Visit 2)*

The Hypoglycemia Confidence Scale (HCS) is further described in Section 7.7.

5.1.8 Change from Baseline in DQOL-brief Total Score

The hypotheses associated with this endpoint are:

- Η₀: μ₁ μ_C = 0
- HA: $\mu_1 \mu_c \neq 0$

where μ_1 and μ_c are the population means of change from Baseline (Visit 2) in DQOL-brief total score after 13 weeks in the Intervention and Control groups, respectively; change from baseline is calculated as follows: *Change from Baseline in DQOL-brief = DQOL-brief (13 weeks) – DQOL-brief (Visit 2)*

The Diabetes Quality of Life-brief is further described in Section 7.7.

5.1.9 Proportion of Participants with T1-DDS MCID (Total Score Improvement ≥0.19) after 13 Weeks

The proportion of participants achieving a minimally clinically important difference (MCID) of ≥ 0.19 points (improvement) on the T1-DDS questionnaire total score at 13 weeks will be compared between treatment groups. [1] Those hypotheses are stated as:

- H₀: $\pi_{I} \pi_{C} = 0$
- $\circ \quad H_A: \pi_I \pi_C \neq 0$

where π_l and π_c are the proportion of participants achieving an improvement of ≥ 0.19 points after 13 weeks in the Intervention and Control groups, respectively.

This endpoint will be considered met if the treatment group fixed effect in the logistic regression is significant at a two-sided significance level of 5%.

5.1.10 Proportion of Participants with DQOL-brief Clinically Meaningful Improvement after 13 Weeks

The proportion of participants achieving a clinically meaningful improvement in the DQOLbrief total score after 13 weeks will be compared between groups [2, 3].

- $H_0: \pi_1 \pi_c = 0$
- $\circ \quad H_A: \pi_I \pi_C \neq 0$

where π_1 and π_c are the proportion of participants achieving a clinically meaning improvement (defined as ≥ 0.5 *standard deviation of change from baseline in the DQOL-brief total score at 13 weeks) in the DQOL-brief total score after 13 weeks in the Intervention and Control groups, respectively.

This endpoint will be considered met if the treatment group fixed effect in the logistic regression is significant at a two-sided significance level of 5%.

5.1.11 Proportion of Participants with HCS Total Score ≥3 after 13 Weeks

The proportion of participants in each treatment group achieving a score of \geq 3 points in the HCS total score after 13 weeks will be compared. Those hypotheses are stated as:

- $H_0: \pi_I \pi_C = 0$
- H_A: π_l π_c ≠ 0

where π_1 and π_c are the proportion of participants achieving a score of ≥ 3 points in the HCS total score after 13 weeks in the Intervention and Control groups, respectively.

This endpoint will be considered met if the treatment group fixed effect in the logistic regression is significant at a two-sided significance level of 5%.

5.2 ANALYSIS OF EXPLORATORY ENDPOINTS (PERIOD 1)

Various exploratory endpoints will be evaluated and compared in the Intervention group versus Control group at the end of the 13-week randomized period.

5.2.1 A1C at 13 Weeks and Improvement from Baseline in A1C

Corelab A1C will be collected at Visit 1 and Visit 8. A1C will be evaluated based on the following exploratory endpoints:

- Proportion of participants with A1C <7% at 13 weeks
- Proportion of participants with A1C <8% at 13 weeks
- Proportion of participants with ≥1% improvement from baseline (Visit 1) in A1C at 13 weeks, where improvement is calculated as follows:

Improvement in A1C = A1C (Visit 1) – A1C (13 weeks)

• Proportion of participants with ≥10 relative percentage point improvement from baseline (Visit 1) in A1C at 13 weeks, where relative percentage point improvement is calculated as follows:

 $Relative improvement in A1C = \frac{A1C (Visit 1) - A1C (13 weeks)}{A1C (Visit 1)} * 100\%$

Proportion of participants with either ≥1% improvement from baseline (Visit 1) in A1C at 13 weeks, or ≥10 relative percentage point improvement from baseline (Visit 1) in A1C at 13 weeks

The endpoints will be compared between groups. The denominator for the calculation of these endpoints includes all participants for whom an A1C at 13 weeks is available. Further, for the endpoints involving improvement in A1C, the A1C at baseline (Visit 1) will also need to be available.

